6.1.3. Protocol Deviations

Important protocol deviations are a subset of protocol deviations that may significantly impact the completeness, accuracy, and/or reliability of the study data or that may significantly affect a subject's rights, safety, or well-being. For example, important protocol deviations may include enrolling subjects in violation of key eligibility criteria designed to ensure a specific subject population or failing to collect data necessary to interpret primary endpoints, as this may compromise the scientific value of the trial.

Important protocol deviations (including deviations related to study inclusion/exclusion criteria, conduct of the trial, patient management or patient assessment) will be summarized. Protocol deviations will be tracked by the study team throughout the conduct of the study. These protocol deviations will be reviewed to identify those considered as important.

Data will be reviewed prior to unblinding and freezing the final Day 29 efficacy database to ensure all important deviations are captured and categorized in the protocol deviations SDTM dataset.

6.1.4. Prior and Concomitant Medications

Concomitant medications will be coded using both the GSK Drug and WHO Drug coding dictionaries. However, they will only be summarized using the GSK Drug dictionary. The summary of concomitant medications will show the number and percentage of subjects taking concomitant medications by Anatomical Therapeutic Chemical (ATC) Level 1 (Body System) and by Ingredient. Standard of care concomitant medications taken for COVID-19 will also be summarized. Multi-ingredient products will be summarized by their separate ingredients rather than as a combination of ingredients. Concomitant Medications will be summarized and listed, while prior medications will be listed.

6.2. Appendix 2 Data Derivations Rule

6.2.1. Criteria for Potential Clinical Importance

This study will not be utilizing lab parameter ranges defining potential clinical important values.

Instead, summaries of worst-case grade increase from baseline grade will be provided for all the lab tests that are gradable by DAIDS 2017 v2.1, if available.

6.2.2. Laboratory Values with DAIDS 2017 v 2.1 Grading

Laboratory parameters of interest	Grade			
	1 Mild	2 Moderate	3 Severe	4 Potentially life-threatening
Absolute Neutrophil Count (ANC), Low (cells/mm ³ ; cells/L) > 7 days of age	800 to 1,000 0.800 x 10 ⁹ to 1.000 x 10 ⁹	600 to 799 0.600 x 10 ⁹ to 0.799 x 10 ⁹	400 to 599 0.400 x 10 ⁹ to 0.599 x 10 ⁹	< 400 < 0.400 x 10 ⁹
Absolute Lymphocyte Count, Low (cell/mm ³ ; cells/L) > 5 years of age (not HIV infected)	600 to < 650 0.600 x 10 ⁹ to < 0.650 x 10 ⁹	500 to < 600 0.500 x 10 ⁹ to < 0.600 x 10 ⁹	350 to < 500 0.350 x 10 ⁹ to < 0.500 x 10 ⁹	< 350 < 0.350 x 10 ⁹
WBC, Decreased (cells/mm ³ ; cells/L) > 7 days of age	2,000 to 2,499 2.000 x 10 ⁹ to 2.499 x 10 ⁹	1,500 to 1,999 1.500 x 10 ⁹ to 1.999 x 10 ⁹	1,000 to 1,499 1.000 x 10 ⁹ to 1.499 x 10 ⁹	< 1,000 < 1.000 x 10 ⁹

Hemoglobin16, Low (g/dL; mmol/L) ≥ 13 years of age (male only)	10.0 to 10.9 6.19 to 6.76	9.0 to < 10.0 5.57 to < 6.19	7.0 to < 9.0 4.34 to < 5.57	< 7.0 < 4.34
Hemoglobin16, Low (g/dL; mmol/L) ≥ 13 years of age (female only)	9.5 to 10.4 5.88 to 6.48	8.5 to < 9.5 5.25 to < 5.88	6.5 to < 8.5 4.03 to < 5.25	< 6.5 < 4.03
Platelets, Decreased (cells/mm3; cells/L)	100,000 to < 125,000 100.000 x 10 ⁹ to < 125.000 x 10 ⁹	50,000 to < 100,000 50.000 x 10 ⁹ to < 100.000 x 10 ⁹	25,000 to < 50,000 25.000 x 10 ⁹ to < 50.000 x 10 ⁹	< 25,000 < 25,000 x 10 ⁹
INR, High (not on anticoagulation therapy)	1.1 to < 1.5 x ULN	1.5 to < 2.0 x ULN	2.0 to < 3.0 x ULN	≥ 3.0 x ULN
ALT or SGPT, High Report only one	1.25 to < 2.5 x ULN	2.5 to < 5.0 x ULN	5.0 to < 10.0 x ULN	≥ 10.0 x ULN
AST or SGOT, High Report only one	1.25 to < 2.5 x ULN	2.5 to < 5.0 x ULN	5.0 to < 10.0 x ULN	≥ 10.0 x ULN
Total Bilirubin, High ≥ 28 days of age	1.1 to < 1.6 x ULN	1.6 to < 2.6 x ULN	2.6 to < 5.0 x ULN	≥ 5.0 x ULN
Potassium, High (mEq/L; mmol/L)	5.6 to < 6.0 5.6 to < 6.0	6.0 to < 6.5 6.0 to < 6.5	6.5 to < 7.0 6.5 to < 7.0	≥ 7.0 ≥ 7.0
Potassium, Low (mEq/L; mmol/L)	3.0 to < 3.4 3.0 to < 3.4	2.5 to < 3.0 2.5 to < 3.0	2.0 to < 2.5 2.0 to < 2.5	< 2.0 < 2.0
Creatinine, High *Report only one	1.1 to 1.3 x ULN	> 1.3 to 1.8 x ULN OR Increase to 1.3 to < 1.5 x subject's baseline	> 1.8 to < 3.5 x ULN OR Increase to 1.5 to < 2.0 x subject's baseline	≥ 3.5 x ULN OR Increase ≥ 2.0 x subject's baseline
Creatinine Clearance or eGFR, Low *Report only one	NA	< 90 to 60 ml/min or ml/min/1.73 m ² OR 10 to < 30% decrease from subject's baseline	< 60 to 30 ml/min or ml/min/1.73 m ² OR 30 to < 50% decrease from subject's baseline	< 30 ml/min or ml/min/1.73 m ² OR ≥ 50% decrease from subject's baseline or dialysis needed

Cardiac Troponin I, High	NA	NA	NA	Levels consistent with myocardial infarction or unstable angina as defined by the local laboratory
--------------------------	----	----	----	--

6.2.3. Study Period

Study phases for Concomitant Medication

Study Phase	Definition
Prior	If medication end date is not missing and is prior treatment start, or if end date is missing but the medication end reference equals BEFORE.
Concomitant	Any medication that is not a prior

Study Treatment Emergent Flag for Adverse Event

Flag	Definition
Study Treatment Emergent	If AE onset date is on or after study treatment start date: 
 • Study Treatment Start Date \leq AE Start Date

NOTES:

- Time of study treatment dosing and start/stop time of AEs should be considered, if collected.
- All Adverse Events tables and figures will be presented for Treatment Emergent AEs. AE listings will display all data.

6.2.4. Study Day and Reference Dates

The safety reference date is the study treatment start date and will be used to calculate study day for all safety measures.

For efficacy, measurements of progressions including: all Hospitalizations, Oxygen Supplementation, and Death will measure from treatment start date to align with safety measurements. Efficacy measurements of all-cause mortality and incidence & duration of ICU, Hospitalization, and Ventilation will calculate study day from date of randomization.

- Ref Date = Missing \rightarrow Study Day = Missing
- Ref Date $<$ First Dose Date \rightarrow Study Day = Ref Date – First Dose Date
- Ref Data \geq First Dose Date \rightarrow Study Day = Ref Date – (First Dose Date) + 1

6.2.5. Multiple measurements at One Analysis Time Point

Where duplicate records exist per scheduled visit/time point/participant (if applicable) in vital signs (including oxygen saturation), laboratory data, and ECG measurements the latest record will be used for summaries.

Subjects having both High and Low values for DAIDS 2017 v2.1 or Normal Ranges at any post-baseline visit for safety parameters will be counted in both the High and Low categories of “Any visit post-baseline” row of related summary tables. This will also be applicable to relevant Potential Clinical Importance (PCI) summary tables where instead of PCI ranges DAIDS 2017 v2.1 or Normal ranges will be considered for reporting of clinically important safety findings.

All data from scheduled and unscheduled visits will be reported in the listings.

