### 8.3.6. Clinical Safety Laboratory Assessments

- See Section 10.2 for the list of clinical laboratory tests to be performed and to the Schedule of Activities (Section 1.3) for the timing and frequency.
- Laboratory assessments at Screening visit will be performed locally at the clinical site as determined necessary by the investigator or as required by local regulations.
- All protocol-required laboratory test performed locally and/or centrally, as defined in Section 10.2, must be conducted in accordance with the laboratory manual and Schedule of Activities (Section 1.3)
  - The investigator must review the laboratory report, document this review, and record any clinically significant changes occurring during the study as an AE. The laboratory reports must be filed with the source documents.
  - Abnormal laboratory findings associated with the underlying disease are not considered clinically significant, unless judged by the investigator to be more severe than expected for the participant's condition.
  - All laboratory tests with values considered by the investigator to be clinically significantly abnormal during participation in the study should be repeated until the values return to normal or baseline or are no longer considered significantly abnormal by the investigator or medical monitor.
    - If clinically significant values do not return to normal/baseline within a period of time judged reasonable by the investigator, the etiology should be identified, and the sponsor notified.
- If laboratory values from non-protocol specified laboratory tests performed at the institution's local laboratory require a change in participant management or are considered clinically significant by the investigator (e.g., SAE or AE), then the results must be recorded.

VIR-7831  
Vir Biotechnology, Inc.

VIR-7831-5008 (GSK Study 217114)  
Amendment 4

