4.5.3. Laboratory Data

Summaries by shift tables of worst-case grade increase from baseline grade will be provided for all the lab tests that are gradable by DAIDS 2017 v2.1. These summaries will display the number and percentage of participants with a maximum post-baseline grade increasing from their baseline grade. Any increase in grade from baseline will be summarized along with any increase to a maximum grade of 2, any increase to a maximum grade of 3 and any increase to a maximum grade of 4. Missing baseline grade will be assumed as grade 0.

For laboratory tests with both low and high graded values, summaries will be provided separately and labelled by direction, e.g., sodium will be summarized as hyponatremia and hypernatremia separately.

Any clinically abnormal laboratory results which are not identified as AEs will be summarised separately, identification of such values will be described in the OPS document.

For lab tests that are not gradable by DAIDS 2017 v2.1, summaries of worst-case changes from baseline with respect to normal range will be generated. Decreases to low, changes to normal or no changes from baseline, and increases to high will be summarized for the worst-case post-baseline. If a participant has a decrease to low and an increase to high during the same time interval, then the participant is counted in both the “Decrease to Low” categories and the “Increase to High” categories.

Summaries and listings for hematology, and chemistry laboratory tests will be produced separately. Liver function laboratory tests will be included with chemistry lab tests.

Separate summary of hepatobiliary laboratory events (if any) including possible Hy’s law cases will be provided in addition to what has been described above.

Possible Hy’s law cases are defined as elevated alanine aminotransferase (ALT) $> 3 \times$ upper limit of normal (ULN), total bilirubin $\geq 2 \times$ ULN or international normalized ratio (INR) > 1.5 . Total bilirubin $\geq 2 \times$ ULN can be within 29 days following the ALT elevation and if direct bilirubin is available on the same day, it must be $\geq 35\%$ of total bilirubin.

The summary will be produced for worst case post baseline only. A plot for maximum post-baseline Total Bilirubin against ALT will also be produced.

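### SAP 6.2.5 keeps only the latest of duplicate records for all summaries, with no exception for the worst-case and maximum-grade safety tables, which can therefore understate the worst grade

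*SAP*

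**What the plan says.** SAP 6.2.5 sets the rule for more than one measurement at an analysis time point. If a participant has duplicates of a vital sign, laboratory test or ECG at the same scheduled visit or time point, "the latest record will be used for summaries". The rule is triggered by duplication within one scheduled visit or time point, and it applies to summaries without distinction. The section adds that listings will show all scheduled and unscheduled data.

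SAP 4.5.3 builds the laboratory safety tables on the worst value: "Summaries by shift tables of worst-case grade increase from baseline grade will be provided" for tests with DAIDS grades, reported as the "number and percentage of participants with a maximum post-baseline grade increasing from their baseline grade". The hepatobiliary summary, including possible Hy's law cases, is also worst case post-baseline, and SAP 4.5.4 does the same for systolic and diastolic blood pressure. SAP 6.2.1 drops ranges of potential clinical importance and relies on the worst-case grade tables instead.

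Protocol 8.3.6 (Amendment 4) says that laboratory values judged clinically significantly abnormal "should be repeated until the values return to normal or baseline", or until they are no longer considered significant. A footnote to Protocol Table 3 asks for creatinine to be repeated within a week if it is high.

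**The concern.** A worst-case table should report the worst valid value that was observed. If one record per visit is selected first and the maximum is taken afterwards, the table reports the worst of the selected values, which is a different quantity.

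For laboratory data the selection is unlikely to be neutral. When a test is repeated because it was abnormal, and repetition stops once it has settled, the last record tends to be the recovered one. The shift, maximum-grade and Hy's law tables could then miss a transient abnormality in the participants whose result prompted a second look. These tables matter because the SAP uses them in place of thresholds of clinical importance.

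**Working it through.** The plan states no figure on this point, so there is none to reproduce. The check has three parts.

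**1. The rule applied to a simple record set.** The grades come from SAP 6.2.2: ALT from 5.0 to below 10.0x ULN is Grade 3, and Grade 1 starts at 1.25x ULN. Take a participant with baseline Grade 0, ALT 6x ULN and then 1.0x ULN at the same scheduled visit, and Grade 0 at the next visit.

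| How the repeat is stored | Values kept under SAP 6.2.5 | Worst grade, SAP rule | Worst grade, all valid records |
|---|---|---|---|
| Same scheduled visit | 0 (visit 1), 0 (visit 2) | 0 | 3 |
| Unscheduled visit, original kept | 3 (visit 1), 0 (visit 2) | 3 | 3 |

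The loss occurs only in the first row. It would also vanish there if another time point held a Grade 3 or worse value.

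**2. Direction.** Baseline is defined separately in SAP 4.1.2, so the duplicate rule acts on the post-baseline side. For any set of valid post-baseline records, the maximum grade over a subset cannot exceed the maximum over the full set. The error in a maximum-grade table is therefore downward or zero. This does not extend to by-visit means or box plots, where the latest record may be higher or lower than the one it replaces.

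**3. Size, as an illustration only.** Let p be the true proportion with a worst-case abnormality, and f the share of those participants whose only such value is overwritten by a same-visit repeat. The documents do not give f, so values from 0 to 50% are assumed. The arm size n = 340 is the planned number in SAP 5.

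- Tabulated proportion = p × (1 − f)
- Expected count = n × p × (1 − f)
- Chance of at least one case in the table = 1 − (1 − p(1 − f))^n

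| p | f | Tabulated proportion | Expected count | Chance of at least one |
|---|---|---|---|---|
| 5% | 0 | 5.0% | 17.0 | about 100% |
| 5% | 10% | 4.5% | 15.3 | about 100% |
| 5% | 25% | 3.75% | 12.75 | about 100% |
| 5% | 50% | 2.5% | 8.5 | about 100% |
| 1% | 0 | 1.0% | 3.4 | 96.7% |
| 1% | 10% | 0.9% | 3.06 | 95.4% |
| 1% | 25% | 0.75% | 2.55 | 92.3% |
| 1% | 50% | 0.5% | 1.7 | 81.8% |

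For example, 340 × 0.05 × (1 − 0.25) = 12.75. With f = 0 nothing is lost, and the documents do not show where f lies.

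**The case against.** The case on the other side is substantial, and much of it stands.

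- **The rule is narrow.** It covers duplicates at one scheduled time point. A repeat ordered after a result has been reviewed, such as creatinine within a week, will often be stored as unscheduled and so fall outside it. The windows in SAP 4.1.1 do not turn such a repeat into a duplicate, because off-day data are used only when nothing was recorded on the day itself. This limits how often the problem can arise.
- **Unscheduled results.** A reader might infer that they go only to listings. SAP 6.2.5 does not say that. It says that listings include them, and it is silent on whether they enter the tables.
- **Abnormal values are not hidden.** Protocol 8.3.6 has clinically significant changes recorded as AEs, Protocol 10.3.2 makes possible Hy's law cases SAEs, SAP 4.5.3 plans a separate summary of clinically abnormal results that did not become AEs, and all values are listed. The mitigation is partial, because AE recording depends on the investigator's judgement and the identification rule for that summary is left to the Output and Programming Specification.
- **Blood pressure.** A reader might extend the repeat-until-normal argument to vital signs. Protocol 8.3.6 covers laboratory tests only, and the successive post-dose readings are separate time points. The missing exception still applies to the blood pressure tables, but no mechanism favouring recovered values is shown for them.
- **The worst-case wording might be read as overriding the general rule.** SAP 4.5.3 provides for the case "If a participant has a decrease to low and an increase to high during the same time interval" and counts both, which suggests that more than one value per interval can count. That supports a clarification. It does not remove the conflict, because SAP 6.2.5 carries no exception and two programmers could build different tables.
- **Technical repeats.** Protocol section 8 allows repeat samples for technical problems, so the later record is sometimes the valid one. This bears on the wording of the fix.
- **Different amendments.** The SAP (version 2.0) rests on Amendment 3, and the repeat-testing text is from Amendment 4. Whether Amendment 3 had the same wording cannot be seen. The missing exception lies in the SAP and does not depend on it.

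**Conclusion.** The point holds as a defect in a stated rule. A bias of known size is not shown. As written, the latest-record rule governs tables that are meant to show the worst value, and it can only leave those tables unchanged or lower them. The conditions are a worse valid value, a better repeat under the same scheduled visit label, and no equal or worse value at another time point. The effect is more plausible for laboratory data than for blood pressure, to the extent that the repeat-testing instruction in Amendment 4 also applied under Amendment 3.

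The primary efficacy result is not affected. The finding concerns the safety tables of the IM versus IV study that this SAP governs. Protocol 9.4 refers to an analysis plan for the safety substudy that was still to be finalised, so carry-over to the substudy is not shown.

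The change is worth making because the conflict is explicit and the correction costs almost nothing.

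**What to change.** Amend SAP 6.2.5 so that the latest-record rule applies only to by-visit descriptive summaries. Then state that the shift, maximum-grade, normal-range worst-case, hepatobiliary/Hy's law and worst-case blood pressure summaries use the worst valid post-baseline value across all scheduled and unscheduled records, duplicates included. Exclude only results documented as technically invalid, and keep those in the listings with the reason. For possible Hy's law cases, apply the timing conditions of SAP 4.5.3 to the same full set of valid records. If the Output and Programming Specification already does this, the SAP should say so. The same wording can be used for the 36-week safety report and for the substudy's analysis plan.

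The cost is a sentence or two of text and a small change to the derivation. Tabulated abnormality rates may rise slightly, and data management must record which repeats replaced a faulty sample.

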6.2.6. Handling of Missing Data

Element	Reporting Detail
General	
 Missing data occurs when any requested data is not provided, leading to blank fields on the collection instrument: 
 These data will be indicated using a “blank” in subject listing displays. Unless all data for a specific visit are missing in which case the data is excluded from the listing. Answers such as “Not applicable”, “Not evaluable” and “Not Done” are not considered to be missing data and should be displayed as such.
Outliers	
 Any subjects excluded from the summaries and/or statistical analyses will be documented along with the reason for exclusion in the clinical study report.
Efficacy Endpoints	
Details around the missing data handling for efficacy endpoints are described in section 6.2.8. In addition:
 
 For the secondary binary endpoint of proportion of subjects who have progression of COVID-19 (i.e., hospitalisation (any duration) OR emergency room visit OR death) through Day 29, missing data will be handled as for the primary endpoint.
Safety Endpoints	
 No missing data imputation will be performed for safety endpoints. Data will be reported as captured.

6.2.7. Handling of Missing and Partial Dates

Element	Reporting Detail
General	
 Partial dates will be displayed as captured in subject listing displays. However, where necessary, display macros may impute dates as temporary variables for sorting data in listings only. In addition, partial dates may be imputed for ‘slotting’ data to study phases or for specific analysis purposes as outlined below. Imputed partial dates will not be used to derive study day, time to onset or duration (e.g., time to onset or duration of adverse events), or elapsed time variables (e.g., time since diagnosis). In addition, imputed dates are not used for deriving the last contact date in overall survival analysis dataset.

Element	Reporting Detail														
Adverse Events	
 Partial dates for AE recorded in the CRF will be imputed using the following conventions: 
 
 Missing start day	 
 If study treatment start date is missing (i.e. subject did not start study treatment), then set start date = 1st of month. Else if study treatment start date is not missing: 
 If month and year of start date = month and year of study treatment start date, then 
 If stop date contains a full date and stop date is earlier than study treatment start date, then set start date= 1st of month. Else set start date = study treatment start date. Else set start date = 1st of month. 	
 
 Missing start day and month	 
 If study treatment start date is missing (i.e. subject did not start study treatment), then set start date = January 1. Else if study treatment start date is not missing: 
 If year of start date = year of study treatment start date, then 
 If stop date contains a full date and stop date is earlier than study treatment start date, then set start date = January 1. Else set start date = study treatment start date. Else set start date = January 1. 	
 
 Missing end day	A '28/29/30/31' will be used for the day (dependent on the month and year)		
 
 Missing end day and month	No Imputation		
 
 Completely missing start/end date	No imputation		
 
 	Missing start day	
 If study treatment start date is missing (i.e. subject did not start study treatment), then set start date = 1st of month. Else if study treatment start date is not missing: 
 If month and year of start date = month and year of study treatment start date, then 
 If stop date contains a full date and stop date is earlier than study treatment start date, then set start date= 1st of month. Else set start date = study treatment start date. Else set start date = 1st of month. 	Missing start day and month	
 If study treatment start date is missing (i.e. subject did not start study treatment), then set start date = January 1. Else if study treatment start date is not missing: 
 If year of start date = year of study treatment start date, then 
 If stop date contains a full date and stop date is earlier than study treatment start date, then set start date = January 1. Else set start date = study treatment start date. Else set start date = January 1. 	Missing end day	A '28/29/30/31' will be used for the day (dependent on the month and year)		Missing end day and month	No Imputation		Completely missing start/end date	No imputation		
Missing start day	
 If study treatment start date is missing (i.e. subject did not start study treatment), then set start date = 1st of month. Else if study treatment start date is not missing: 
 If month and year of start date = month and year of study treatment start date, then 
 If stop date contains a full date and stop date is earlier than study treatment start date, then set start date= 1st of month. Else set start date = study treatment start date. Else set start date = 1st of month. 														
Missing start day and month	
 If study treatment start date is missing (i.e. subject did not start study treatment), then set start date = January 1. Else if study treatment start date is not missing: 
 If year of start date = year of study treatment start date, then 
 If stop date contains a full date and stop date is earlier than study treatment start date, then set start date = January 1. Else set start date = study treatment start date. Else set start date = January 1. 														
Missing end day	A '28/29/30/31' will be used for the day (dependent on the month and year)														
Missing end day and month	No Imputation														
Completely missing start/end date	No imputation														
Concomitant Medications	
 Partial dates for any concomitant medications recorded in the CRF will be imputed using the following convention: 
 
 Missing start day	 
 If study treatment start date is missing (i.e. subject did not start study treatment), then set start date = 1st of month. Else if study treatment start date is not missing: 
 If month and year of start date = month and year of study treatment start date, then 
 If stop date contains a full date and stop date is earlier than study 		
 
 	Missing start day	
 If study treatment start date is missing (i.e. subject did not start study treatment), then set start date = 1st of month. Else if study treatment start date is not missing: 
 If month and year of start date = month and year of study treatment start date, then 
 If stop date contains a full date and stop date is earlier than study 												
Missing start day	
 If study treatment start date is missing (i.e. subject did not start study treatment), then set start date = 1st of month. Else if study treatment start date is not missing: 
 If month and year of start date = month and year of study treatment start date, then 
 If stop date contains a full date and stop date is earlier than study 														

Element	Reporting Detail
	
treatment start date, then set start date= 1st of month.
 
 ▪ Else set start date = study treatment start date. • Else set start date = 1st of month. 
Missing start day and month
 
 • If study treatment start date is missing (i.e. subject did not start study treatment), then set start date = January 1. • Else if study treatment start date is not missing: 
 ◦ If year of start date = year of study treatment start date, then 
 ▪ If stop date contains a full date and stop date is earlier than study treatment start date, then set start date = January 1. ▪ Else set start date = study treatment start date. • Else set start date = January 1.
	Missing end day
	Missing end day and month
	Completely missing start/end date
Oxygen Supplementation	
Completely missing end date
 
If the end date is missing and subsequent record exists and is not missing the start date, impute the missing end date as the start date of the subsequent record.
 
If end date is missing and no subsequent record exists, the method of oxygen supplementation will be considered ongoing at time of database extraction.

Age	Age will be imputed from year of birth. The calculation will use 30 June as the day and month and will calculate the age relative to Screening date.

